12.1 Data Monitoring Committee

The specific activities of the DMC will be governed by a charter which will define the DMC's membership, meeting frequency, procedures/conduct, and requirements for reporting its observations to the sponsor.

To ensure safety oversight throughout the trial, the DMC will review safety and preliminary efficacy data and provide recommendations to the Sponsor as described below.

The DMC will convene at the following times and for the following activities during the trial:

- Review safety data for at least 5 subjects who received IMR-687 at the lower dose and make recommendation as to the inclusion of the higher dose.
- Review safety data to confirm acceptable safety and tolerability of the higher dose of IMR-687. Make recommendation as to whether the dose level(s) could be modified; the proposed modification would occur only after a substantial protocol amendment was submitted to and approved by any applicable regulatory authorities.
- At any time during the trial—upon request by the Sponsor, medical monitor, or DMC—should a concern arise from emerging safety data for which DMC review and assessment is desired. This includes the emergence of a frequency or pattern of AEs or serious adverse events (SAEs) that suggest an unexpected or otherwise concerning safety signal.

The DMC may review the following subject data, depending on the scope of the meeting, and may recommend to continue the study as planned, modify the study, or terminate the study for safety or lack of efficacy concerns:

- Unblinded safety, preliminary efficacy, and PK data, which may include TEAEs, SAEs, clinical laboratory test results, vital signs, and other relevant data for all subjects randomized.
- Additionally, the DMC chairperson will receive copies of all SAE reports for ongoing review during the trial. The DMC chairperson may forward the SAE reports to the full DMC if he/she feels that their immediate input on, or awareness of the SAE would be helpful.

All assessments and decisions by the DMC will be documented in writing as noted in the DMC charter and prior to any resultant changes to the study unless their immediate implementation is considered necessary for subject safety. The composition of the DMC will be detailed in the DMC charter.

13.0 Statistical Methods

All statistical analyses will be conducted using SAS Version 9.4.

Descriptive summary statistics will be provided for demographics, disposition, and IMR-687 exposure. The number and percentage of subjects who discontinue from the study, along with reasons for discontinuation will be tabulated.

Continuous data will be summarized using descriptive statistics (number of subjects, mean, SD, median, first quartile (Q1), third quartile (Q3), minimum, and maximum, %CV). Frequencies and percentages will be used for summarizing categorical (discrete) data. For summaries of categorical variables, counts and percentages are based on the number of subjects in the analysis set unless otherwise specified.

All statistical tests and resulting p-values will be reported as 2-sided. Confidence intervals, when presented, will be constructed at the two-sided 95% level, unless noted otherwise.

P-values will be presented to 4 decimal places with values less than 0.0001 presented as “<0.0001” and p-values greater than 0.9999 presented as “>0.9999”.

Means, medians, Q1s, and Q3s will be presented to 1 or more decimal places than the recorded data. The SDs will be presented to 2 more decimal places than the recorded data. Confidence intervals about a parameter estimate, minimums, and maximums will be presented using the same number of decimal places as the parameter estimate. Percentages will be presented to 1 decimal place.

A month is operationally defined to be 30.4375 days. A year is defined to be 365.25 days. A week is defined to be 7 days.

Where specified, there will be pair-wise comparisons between IMR-687 lower dose vs. placebo, IMR-687 higher dose vs. placebo and IMR-687 pooled dose vs. placebo.

Separate table and figure outputs will be produced for each TDT/NTDT population. The TDT population may be unblinded and reported at a separate time from the NTDT population depending on enrollment. If this occurs the blind of the unfinished population will be preserved. Listings will include both the TDT and NTDT populations with the TDT population presented first in the listing

13.1 Subject Disposition

The number of subjects screened, screen failed, randomized, and treated in the study will be presented, together with the number and percentage of subjects who completed 24 weeks of treatment, completed 36 weeks of treatment, discontinued study drug, and discontinued from the study will be tabulated. The primary reason for screen failure, study drug discontinuation, and study discontinuation will also be tabulated.

Subjects who completed 24 weeks of treatment are defined as either 1) answered “Yes” to the “Did the subject take study drug dose during clinic visit?” question at the Week 24 visit, or later, on the Study Drug Administration eCRF, or 2) have a non-missing “Start Date of Dose From This Bottle” or “Date of Last

Dose for this Bottle" on the Study Drug Accountability eCRF that is on or after the Week 24 visit. Subjects who completed 36 weeks of treatment are defined similarly relative to the week 36 visit.

Percentages for screen failed, primary reason for screen failure, and randomized will be based on all subjects screened. Percentages for number of subjects treated in the study will be based on all randomized subjects. Percentages for number of subjects who completed 24 weeks of treatment, number of subjects who completed 36 weeks of treatment, number of subjects who discontinued study drug, primary reason for study drug discontinuation, number of subjects discontinued from the study, and the primary reason for study discontinuation will be based on all treated subjects.

Summaries will be based on all subjects screened and tabulated for each treatment arm and the total and will be reported separately for TDT and NTDT subjects.

Tabulation of the number and percentage of subjects included in each analysis set will be provided. All percentages will be based on all randomized subjects, for each treatment arm and the total, and will be reported separately for TDT and NTDT subjects.

Details regarding randomization assignments, replacement of randomized subjects, subjects who discontinued study drug and/or study, and subject analysis sets will be reported in by-subject listings.

13.2 Important Protocol Deviations

Prior to the database lock for the primary analysis, the Sponsor or designee medical and statistics personnel will identify and review any deviations from the study protocol. Any protocol deviations that might significantly affect the completeness, accuracy, and/or reliability of the study data or that might significantly affect a subject's rights, safety, or well-being will be classified as important protocol deviations (FDA, ICH, 2013, January).

Tabulation of the number and percentage of subjects with important protocol deviations by center and category within each treatment arm will be presented on the Safety Analysis Set separately for each population. Categories will be sorted alphabetically, and deviations within each category will be sorted alphabetically. Categories will include:

- Deviations related to study inclusion or exclusion criteria
- Receipt of any prohibited therapies as defined in the protocol
- Significant deviations in study drug administration
- Subjects were not withdrawn after developing withdrawal criteria during the study

Details for protocol deviations for subjects in the Safety Analysis Set will be provided in protocol deviation and important protocol deviation data listings.

13.3 Treatment

13.3.1 Extent of Study Drug Exposure and Drug Accountability

A summary of exposure and compliance, to be reported on the Safety Analysis Set, will include the total number of tablets taken, compliance (%), total exposure (mg), average daily dose (mg/day), duration of exposure (in weeks), and incidence and duration of dose interruption. These parameters will be calculated as follows:

- Duration of exposure (in weeks) will be calculated as [(date of last dose of study medication – date of first dose of study medication + 1)/7]. The date of first dose of study medication will be collected from the Study Drug Administration CRF page and the date of last dose of study medication will be collected from the End of Treatment CRF page. If there is no date for end of treatment on the End of Treatment CRF page, the last available dose date will be used. See Appendix 3 for a complete set of data handling rules.
- Total number of tablets taken = total number of tablets dispensed – total number of tablets returned. The total number of tablets dispensed and returned will be collected from Study Drug

Accountability CRF Page. They are to be collected at study visits and will be summed over the whole study treatment period.

- Total exposure (mg) of IMR-687 = Total number of tablets taken * tablet dose level (100/150/200 mg). IMR-687 will be supplied as 100, 150, or 200 mg white tablets in the study. In the lower dose group (≥ 3.0 to ≤ 5.0 mg/kg), subjects weighing <60 kg will be dispensed 100 mg tablets and those weighing ≥ 60 kg will be dispensed 150 mg tablets. In the higher dose group (>4.5 to ≤ 6.7 mg/kg), subjects weighing <60 kg will be dispensed 150 mg tablets and those weighing ≥ 60 kg will be dispensed 200 mg tablets. The dose regimen for all subjects is 2 tablets once daily. The weight at the baseline will be used to establish the dose level and the same dose level will be used throughout the trial.
- Incidence and duration of dose interruption: as collected from the IP Interruptions CRF page.
- Overall compliance (%) = $[(\text{total number of tablets dispensed} - \text{total number of tablets returned}) / \text{duration of exposure (days)}] \times 100$.
- Average daily dose (mg/day) = total exposure (mg) / duration of therapy (days).

Additional considerations and data handling in exposure and drug accountabilities may be needed for the DMC, IA, and final analysis when some of drug dosing and accountability information is deemed incomplete. See Appendix 3 for a complete set of data handling rules for drug exposure and accountability.

The same tabulation will be generated for the PP Analysis set if it is not the same as the Safety Analysis Set.

Details of the administration of study drug, including randomized and actual treatment, start date and time of each dose, dose per administration, and date, time, and composition of last meal will be listed on the Safety Analysis Set.

Details of study drug accountability including date dispensed, date returned, amount returned, and compliance per dosing period (in %, as collected directly from CRF), overall compliance (in %, for the whole duration of study drug exposure, as calculated as above) will be listed based on the Safety Analysis Set.

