### **9.3. Packaging and Labeling**

Finished tablets will be packaged in round, 60 cc high-density polyethylene bottles with a polypropylene cap. Each bottle contains 84 tablets. The bottles are induction sealed and capped. Each bottle will be labelled with a suitable Annex 13 country compliant product label.

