## 9.6. Treatment Compliance

The investigator or designee must ensure that all subjects are adequately informed of study drug administration requirements for compliance/adherence with the study protocol.

Treatment compliance/adherence with scheduled oral administration of study drug will be assessed at the study site starting at Week 3 for TDT subjects or Week 4 for NTDT subjects; all study drug administration will be documented on the appropriate pages of the eCRF. Subjects falling below an 80% treatment compliance rate between consecutive visits will be reported as a protocol deviation.

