IMR-687 will be supplied as 100, 150, or 200 mg white tablets. Subjects will be advised to take two IMR-687 tablets with food QD for 36 weeks. To maintain appropriate exposures, 60 kg will be used as the weight gate for tablet strength. Subjects in the lower dose group weighing <60 kg will be dispensed 100 mg tablets and those weighing ≥ 60 kg will be dispensed 150 mg tablets (daily dose 200 mg and 300 mg, respectively). Subjects in the higher dose group weighing <60 kg will be dispensed 150 mg tablets and those weighing ≥ 60 kg will be dispensed 200 mg tablets (daily dose 300 mg and 400 mg, respectively). The different doses of IMR-687 are visually identical in tablet form.

Placebo will consist of tablets containing matrix absent IMR-687 and will be identical in appearance to the IMR-687 tablets. Subjects will be advised to take two placebo tablets orally with food QD for 36 weeks.

[figure not shown]
Subjects will be directed to take study drug (either IMR-687 or placebo) with food, but if a subject does not do so, it will not be considered a protocol deviation.

Interim analyses will be conducted at each of the following milestones:

- Approximately 15 subjects in the NTDT population have completed 12 weeks of treatment
- Approximately 30 subjects in the TDT population have completed 24 weeks of treatment
- Approximately 30 subjects in the NTDT population have completed 24 weeks of treatment
- Approximately 60 subjects in the TDT population have completed 24 weeks of treatment

- Approximately 60 subjects in the NTDT population have completed 24 weeks of treatment

Figure 1: Overview of Study Design and Dose Groups

* Prior to the introduction of IMR-687 higher dose, the DMC will review safety data for at least 5 subjects who received IMR-687 lower dose. If the DMC recommends inclusion of the higher dose, randomization across 3 dose groups will then proceed as shown. The DMC may request additional data and/or meeting(s) in order to make its recommendations. During study conduct under Protocol Version 4.0, the DMC approved the opening of enrollment in the higher dose IMR-687 group, which went into effect on 01 February 2021.

Refer to Protocol Section 5.1 for additional details on the dose groups.

Note: There will be an additional interim analysis (IA 0.5) for approximately 15 subjects in the NTDT population that have completed 12 weeks of treatment.

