13. Duration of Exposure (days)	Duration of Exposure (days)	Exposure is defined as (Date of the last dose of the study drug – Date of first dose of the study drug + 1).
14. General	Conversion of Duration in Days to Duration in Years/Months/Days	
Duration in Years = Duration in Days/365.25
 
Duration in Months = Duration in Days/30.4375
 
Duration in Weeks = Duration in Days/7

15. Hard coding	Hard coding for data analysis	Hard Coding is not allowed during data analysis unless if agreed in writing by Imara.

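### SAP 13.3.1 divides tablets taken by days although the regimen is two tablets a day, so overall compliance is reported at twice its true value

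*SAP*

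**What the plan says.** SAP section 13.3.1 defines tablets taken as the number dispensed minus the number returned. It then sets overall compliance (%) equal to that count divided by the duration of exposure in days, times 100. In the same list of definitions, under total exposure, it says: "The dose regimen for all subjects is 2 tablets once daily". Protocol section 9.2 gives two tablets once daily for active drug and for placebo. SAP section 8.0 converts this to mg for the lower dose group, on 100 mg and 150 mg tablets: "daily dose 200 mg and 300 mg, respectively".

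Appendix 3 of the SAP counts exposure in calendar days ("Exposure is defined as (Date of the last dose of the study drug", minus the first dose date, plus 1). It has no term for tablets per day.

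The result is used in two places:

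- **Summary.** The exposure and compliance table is produced on the Safety Analysis Set, and "The same tabulation will be generated for the PP Analysis set if it is not the same as the Safety Analysis Set".
- **Listing.** The accountability listing shows "overall compliance (in %, for the whole duration of study drug exposure, as calculated as above", next to compliance per dosing period, which is taken directly from the CRF.

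On a separate matter, the total-exposure definition in section 13.3.1 describes tablet strengths with a 60-kg gate only and says baseline weight sets the dose level. Protocol section 5.1 says the study began with a 67-kg gate and moved to 60 kg from Version 5.0.

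**The concern.** Compliance should be the tablets taken as a share of the tablets due. With two tablets due each day, the number due is 2 × days. Dividing by days alone gives tablets per day, which the SAP then multiplies by 100 and labels a percentage.

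The direction of the error matters. A subject who missed half the study drug appears fully compliant. A reader who compares the listed overall figure with the protocol's 80% benchmark would pick out only subjects whose true adherence is below 40%. In the listing, the doubled figure would also conflict with the per-period values beside it if the CRF values allow for two tablets a day. Safety and tolerability is the primary objective, and adherence is part of what a reader needs to interpret it.

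**Working it through.** The documents state no numerical compliance figure to reproduce, so the formula itself is tested.

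**Inputs**

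- Tablets due per day: 2 (SAP 13.3.1; Protocol 9.2).
- Duration: Day 1 to Day 252, the scheduled Week 36 visit = 252 days (schedules of assessments; day count per Appendix 3).
- Tablets due: 2 × 252 = 504. As a cross-check on packaging, "Each bottle contains 84 tablets" (Protocol 9.3). At two a day a bottle lasts 84/2 = 42 days, and 252/42 = 6 bottles = 504 tablets.

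**Formulas**, with T = tablets dispensed minus returned and D = days of exposure

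- SAP: T / D × 100
- With the regimen included: T / (2 × D) × 100

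| True adherence | T over 252 days | SAP formula | With factor 2 |
|---|---|---|---|
| 100% | 504 | 504/252 = 200% | 504/504 = 100% |
| 80% | 403.2 | 403.2/252 = 160% | 403.2/504 = 80% |
| 50% | 252 | 252/252 = 100% | 252/504 = 50% |
| 40% | 201.6 | 201.6/252 = 80% | 201.6/504 = 40% |

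Since T = 2 × D × adherence, D cancels and the SAP value is exactly 2 × adherence for any duration. Using 253 days gives the same percentages.

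**Check within the same table.** A fully adherent subject on 150 mg tablets has total exposure 504 × 150 = 75,600 mg. Average daily dose is 75,600/252 = 300 mg/day, which equals the planned daily dose in SAP 8.0. The compliance line for the same subject reads 200%. The dose line reflects two tablets a day and the compliance line does not.

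**Outputs affected.** If the exposure summary listed in SAP Tables 3 and 4 is this table, it is due at IA 1.0, IA 2.0 and final for TDT (3), and at IA 0.5, 1.0, 2.0 and final for NTDT (4). That makes 7 Safety-set outputs.

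**Weight gate (conditional).** This matters only if the programming derives tablet strength from the 60-kg rule for subjects dispensed under the 67-kg gate. Assume also that tablet strengths were the same under Version 4.0 and were not switched later. For subjects of 60 to <67 kg, mg exposure would then be overstated by 150/100 = 1.50 (50%) in the lower dose group and 200/150 = 1.33 (33%) in the higher dose group. The same-strength assumption agrees with the stated Version 4.0 ranges only to rounding: 200/67 = 2.99, 200/45 = 4.44, 300/67 = 4.48, 300/45 = 6.67 mg/kg, against 3.0 to 4.5 and 4.5 to 6.7.

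**The case against.** The best case against giving this weight is that the error reveals itself and has no consequence downstream. A uniform doubling puts an arm with ordinary adherence near 200%, which nobody would accept. The same summary shows average daily dose, where a half-adherent subject on 150 mg tablets would show 150 mg/day against a planned 300. The protocol's deviation rule is applied by interval, not overall: "Subjects falling below an 80% treatment compliance rate between consecutive visits will be reported as a protocol deviation". Nothing shows that it uses this formula. No endpoint or analysis set cites overall compliance. The mention of exposure summaries in Tables 3 and 4 does not name compliance, so the count of seven outputs is conditional.

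Most of this stands, and it limits the scope. It does not rescue the formula. Section 13.3.1 allows extra data handling only for incomplete dosing or accountability records, which does not cover a wrong denominator. An arm mean near 200% would be noticed, but a single listing line of 100% for a half-adherent subject could pass. The SAP is final at Version 1.0, so a silent correction in programming would make the output depart from its specification.

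The objection to the weight-gate point is stronger. The 60-kg text can be read as describing dispensing only. The section quotes the dose ranges pooled over both protocol versions, and the administration listing includes dose per administration. Heavier subjects also fall outside the stated ranges (400/90 = 4.44 and 300/105 = 2.86 mg/kg), so those ranges cannot confirm the Version 4.0 tablet strengths. Going by document dates, the higher dose was open under the earlier gate for about six weeks (01 February to 15 March 2021). This point therefore carries low to moderate confidence.

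**Conclusion.** The formula is wrong as written and doubles every overall compliance value. This rests only on the two-tablet regimen and the day count, both stated in the documents, so confidence is high. The effect is confined to the overall compliance line in the exposure summary and the accountability listing. Total exposure, average daily dose and CRF per-period compliance do not use this denominator. It should be corrected, but it does not threaten the trial's comparisons.

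The weight-gate text is a minor inconsistency between SAP 13.3.1 and Protocol 5.1. It would misstate mg exposure only under the three assumptions given above (derivation from the 60-kg rule, same strengths, no later switch), and the number of subjects concerned is not given.

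**What to change.** Replace the definition in SAP 13.3.1 with: overall compliance (%) = (tablets dispensed − tablets returned) / (2 × duration of exposure in days) × 100. The cost is one factor in one formula, recorded as an SAP change.

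State whether permitted holds and reductions change the expected count. Either choice is acceptable and neither is needed for the correction. Under Protocol Table 4, a 7-day hold (7 × 2) or 14 days with one tablet fewer (14 × 1) removes 14 tablets. Otherwise full intake then gives 490/504 = 97.2% if no adjustment is made.

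Separately, reconcile the 60-kg text in SAP 13.3.1 with the 67-kg gate in Protocol 5.1. Add one sentence saying that total exposure uses the tablet strength recorded as dispensed, which the bottle codes in Protocol 10.2 identify.

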Clinical safety and tolerability data are available from Study IMR-SCD-101 in healthy volunteers for IMR-687 administered at doses up to 6 mg/kg/day in a fasted single ascending dose (SAD) portion (Part A) and at doses up to 4.5 mg/kg/day for 7 days in a fed multiple ascending dose (MAD) portion (Part C), as well as from the phase 2a study in fed subjects with sickle cell disease (IMR-SCD-102). Based on these data, exposure ranges from 3 mg/kg to approximately 6 mg/kg is expected to be tolerable, especially if taken with food because administration with food appears to reduce both the incidence and severity of nausea and/or gastrointestinal (GI) pain. The onset of nausea in the healthy volunteer study was rapid (between 30 to 120 minutes) and generally lasted 2 to 8 hours and was mild nature at doses  $\leq$ 4.5 mg/kg (lower dose). These potential AEs of nausea, upper GI pain, and emesis are easily monitorable and are self-limited if dosing is stopped. Furthermore, following qd dosing for 7 days in fed healthy volunteers, steady state was achieved before Day 7. Exposure (area under the concentration-time curve [AUC]) in healthy volunteers increased in a near dose-proportional manner (a 4.1-fold increase for a 4.5-fold change in dose [see Section 4.1.3.1 of the protocol]), and the mean exposure (AUC from time 0 to 24 hours [AUC0-24]) at 4.5 mg/kg on Day 7 was 26.3  $\mu$ g $\cdot$ h/mL, which is approximately 3.3-fold below the Week 39 exposure (AUC0-24) in the female dog (most conservative species/gender) at the respective no observed adverse effect level (NOAEL) in the repeat-dose toxicology study. Furthermore, the predicted Day 1 exposure in the higher dose arm of up to 6.7 mg/kg is 32.0  $\mu$ g $\cdot$ h/mL, which remains approximately 2.7-fold below the Week 39 exposure (AUC0-24) in the female dog (most conservative species/gender).

This study initially imposed a minimum weight threshold of 45 kg and a 67-kg weight gate for tablet strength to ensure that subjects in the lower dose IMR-687 group received a dose equating to no more than the 4.5 mg/kg evaluated in the MAD part of the healthy volunteer study. Subsequently, the DMC approved the opening of enrollment in the higher dose IMR-687 group (up to 6.7 mg/kg). Having established safety and tolerability of the lower dose, the DMC also approved a change in weight gate

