### **Independent Data Monitoring Committee Oversight**

This study initially imposed a minimum weight threshold of 45 kg and a 67-kg weight gate for tablet strength to ensure that subjects in the lower dose IMR-687 group received a dose equating to no more than the 4.5 mg/kg evaluated in the MAD part of the healthy volunteer study. Subsequently, the Data Monitoring Committee (DMC) approved the opening of enrollment in the higher dose IMR-687 group (up to 6.7 mg/kg). Having established safety and tolerability of the lower dose, the DMC also approved a change in weight gate to 60 kg and the resultant modified dose range of up to 5.0 mg/kg in the lower dose group (with the minimum weight threshold of 45 kg unchanged). Starting from Protocol Version 5.0, subjects in the IMR-687 lower dose group will receive  $\geq 3.4$  to  $\leq 5.0$  mg/kg and subjects in the higher dose group will receive  $>5.0$  to  $\leq 6.7$  mg/kg; no subject will receive more than 6.7 mg/kg. Under Protocol Version 4.0, the exposure ranges were  $\geq 3.0$  to  $\leq 4.5$  mg/kg in the lower dose group and  $>4.5$  to  $\leq 6.7$  mg/kg in the higher dose group. Therefore, the overall exposure ranges during the course of the study are  $\geq 3.0$  to  $\leq 5.0$  mg/kg and  $>4.5$  to  $\leq 6.7$  mg/kg and are presented as such hereafter.

For this first study evaluating IMR-687 in subjects with  $\beta$ -thalassemia, the DMC has noted some of the related pathology that is shared with patients who have SCD. The shared manifestations include chronic anemia, fatigue, delayed growth, cerebral ischemia, splenomegaly, gallstones, pulmonary hypertension, and leg ulcers. In the phase 2a study in adult subjects with SCD (IMR-SCD-102), IMR-687 has been shown to be well tolerated, with initial evidence of PD effects. The DMC has reviewed interim results from this study and is supportive of the dose exposure and duration of treatment in this first  $\beta$ -thalassemia study.

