## 7. INVESTIGATIONAL PLAN

### 7.1. Overall Study Design

This is a phase 2 randomized, double-blind, placebo-controlled study to evaluate the safety, tolerability, PK, and PD of IMR-687 (PDE9 inhibitor) administered qd for 36 weeks in 2 populations of adult subjects with  $\beta$ -thalassemia: Population 1 (TDT subjects) and Population 2 (NTDT subjects). A schematic of the study is provided in [Figure 1](#).

[figure not shown]
This study will enroll approximately 120 subjects with  $\beta$ -thalassemia (60 subjects with TDT and 60 subjects with NTDT), aged 18 through 65 years. This study consists of a retrospective data collection period, a screening period, a double-blind treatment period, and safety follow-up period. During the screening period of up to 28 days, subjects will provide informed consent and be evaluated on eligibility criteria as stated in [Section 8.1](#) and [Section 8.2](#).

Subjects will receive either IMR-687 (lower dose [ $\geq 3.0$  to  $\leq 5.0$  mg/kg] or higher dose [ $>4.5$  to  $\leq 6.7$  mg/kg]; the precise exposure ranges for different groups of subjects are dependent on the weight gate for tablet strength as summarized in [Section 5.1](#)) or placebo in a blinded fashion. Subjects will be randomly assigned in a 2:1 ratio to receive either IMR-687 lower dose or placebo. Prior to the introduction of IMR-687 higher dose, the DMC will review safety data for at least 5 subjects who received IMR-687. If the DMC recommends inclusion of the higher dose, randomization will then proceed in a 1:2:1 ratio (IMR-687 lower dose, IMR-687 higher dose, or placebo). The DMC may request additional data and/or meeting(s) in order to make the recommendation on whether to move forward with inclusion of the higher dose. During study conduct under Protocol Version 4.0, the DMC approved the opening of enrollment in the higher dose IMR-687 group, which went into effect on 01 February 2021.

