### 10.2. Blinding

To ensure that the subject and site are blinded with respect to each subject's treatment assignment, placebo tablets and tablets for each dose level of IMR-687 are identical in appearance and are supplied in identical packaging. Each bottle will contain a code that identifies the contents as either 100 mg IMR-687, 150 mg IMR-687, 200 mg IMR-687, or placebo.

Every attempt should be made to preserve the integrity of study drug blinding. Except for cases of emergency unblinding, as described in Section 10.4, the randomization code will remain unbroken for subjects and study personnel at the site until the database has been locked for each study population. The blinded sponsor and CRO study team members will only be unblinded to the analysis results at the conclusion of the study (e.g., database lock).

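### SAP 13.3.1 applies a 60 kg tablet-strength cut-off to every subject, so recorded exposure is overstated for IMR-687 subjects of 60 to <67 kg who started under the 67 kg cut-off

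*SAP*

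**What the plan says.** **SAP 13.3.1.** Total exposure is tablets taken multiplied by tablet strength (100, 150 or 200 mg). Average daily dose is that total divided by days of therapy. The section gives one strength rule, split at 60 kg: 100 or 150 mg tablets in the lower-dose arm and 150 or 200 mg in the higher-dose arm, two tablets a day. It continues: "The weight at the baseline will be used to establish the dose level and the same dose level will be used throughout the trial". The arms are labelled ≥3.0 to ≤5.0 and >4.5 to ≤6.7 mg/kg. Protocol 5.1 describes these as the ranges over the whole study, so the rule covers subjects treated under Version 4.0.

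**Protocol 5.1 and Synopsis, Study Rationale.** "This study initially imposed a minimum weight threshold of 45 kg and a 67-kg weight gate for tablet strength". The aim was that lower-dose subjects "received a dose equating to no more than the 4.5 mg/kg evaluated in the MAD part of the healthy volunteer study". Later, "the DMC also approved a change in weight gate to 60 kg and the resultant modified dose range of up to 5.0 mg/kg". The ranges are given by version. "Under Protocol Version 4.0, the exposure ranges were" 3.0 to 4.5 mg/kg (lower) and >4.5 to 6.7 mg/kg (higher). "Starting from Protocol Version 5.0, subjects in the IMR-687 lower dose group will receive" 3.4 to 5.0 mg/kg, and the higher-dose group >5.0 to 6.7 mg/kg.

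**Timing.** Protocol 7.1: "During study conduct under Protocol Version 4.0, the DMC approved the opening of enrollment in the higher dose IMR-687 group", effective 01 February 2021. SAP 13.6.5 dates Version 5.0 at 15 Mar 2021.

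**What the SAP leaves out.** The 67 kg cut-off appears nowhere in it. Section 8.0 gives only 60 kg, and Appendix 3 has no rule for tablet strength by protocol version.

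**The concern.** The two cut-offs give different tablet strengths for anyone weighing 60 to <67 kg. If the SAP's single rule is programmed as written, a subject dispensed under the 67 kg cut-off is credited with the larger tablet. Total mg and mg/day then describe drug that the subject did not take, always in the upward direction. These are the plan's own summaries of how much drug was received, in a study whose primary objective is safety and tolerability, so they should be right for every subject.

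There is a second conflict. Protocol 5.1 can be read as moving subjects already on treatment to the new range at Version 5.0, while SAP 13.3.1 says the dose level never changes. The documents do not settle which applies.

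**Working it through.** **Inputs.** Two tablets a day and the strengths in SAP 13.3.1 and Protocol 9.2, giving 200 or 300 mg/day (lower arm) and 300 or 400 mg/day (higher arm); minimum weight 45 kg; cut-offs of 67 kg and 60 kg and the ranges by version from Protocol 5.1.

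**Step 1: reproduce the stated ranges.** mg/kg = daily dose / weight.

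| Cut-off | Arm | At 45 kg | Just below cut-off | At cut-off | Stated range |
|---|---|---|---|---|---|
| 67 kg | lower | 200/45 = 4.44 | 200/66.99 = 2.99 | 300/67 = 4.48 | 3.0 to 4.5 |
| 67 kg | higher | 300/45 = 6.67 | 300/66.99 = 4.48 | 400/67 = 5.97 | >4.5 to 6.7 |
| 60 kg | lower | 200/45 = 4.44 | 200/59.99 = 3.33 | 300/60 = 5.00 | 3.4 to 5.0 |
| 60 kg | higher | 300/45 = 6.67 | 300/59.99 = 5.00 | 400/60 = 6.67 | >5.0 to 6.7 |

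The upper limits and the Version 4.0 lower limits reproduce to rounding. The Version 5.0 lower limit of 3.4 does not (3.33), but nothing below depends on it.

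**Step 2: infer the Version 4.0 strength at 60 to <67 kg.** The Version 4.0 tablet table is not printed.

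- Lower arm: 300 mg exceeds 4.5 mg/kg at any weight below 300/4.5 = 66.7 kg. The 4.5 mg/kg limit therefore implies 200 mg in almost the whole band. This inference is firm.
- Higher arm: 400 mg at 60 kg is 6.67 mg/kg, so the 6.7 limit does not exclude it. The support is that the stated lower limit moves from >4.5 to >5.0 as the cut-off moves, matching 300/67 = 4.48 and 300/60 = 5.00. The printed lower limits are not true minima (400 mg falls to 5.0 mg/kg at 80 kg, since 400/80 = 5.0), so this inference is weaker.

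**Step 3: SAP rule against inferred dispensing, Version 4.0, 60 to <67 kg.**

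| Arm | Dispensed (inferred) | SAP rule | Ratio | Over 252 days, full compliance |
|---|---|---|---|---|
| lower | 200 mg/day | 300 mg/day | 300/200 = 1.50 | 75,600 v 50,400 mg |
| higher | 300 mg/day | 400 mg/day | 400/300 = 1.33 | 100,800 v 75,600 mg |

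Below 60 kg, and at 67 kg or more, the two cut-offs give the same strength and there is no error.

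**Step 4: if such subjects were re-dispensed at Version 5.0 (assumption).** With a switch at week k of 36, the true mean daily dose is [k × old + (36 − k) × new]/36.

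- k = 12: lower (12 × 200 + 24 × 300)/36 = 266.7, and 300/266.7 gives +12.5%; higher 366.7, and 400/366.7 gives +9.1%.
- k = 24: lower 233.3, +28.6%; higher 333.3, +20.0%.

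**Step 5: effect on an arm mean.** The affected share is not in the documents. Purely for scale, with no switch, a share of 5% to 20% of an arm raises its mean by 0.05 × 100 = 5 to 0.20 × 100 = 20 mg/day.

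**The case against.** The best defence is that SAP 13.3.1 repeats the dispensing text of Protocol 9.2, and that the baseline-weight sentence only means strength is not revised when weight changes. Nothing tells the programmer to ignore what was dispensed, and the SAP also lists dose per administration for each subject. That makes the wording less than conclusive, but it does not rescue the summary. Read as a description of dispensing, the text is untrue for Version 4.0 subjects and leaves no rule for their strength. The listing does not feed the formulas for total mg or mg/day.

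Three limits stand:

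- The Version 4.0 strengths are inferred.
- The higher arm opened on 01 February 2021 and Version 5.0 is dated 15 Mar 2021, about six weeks later (longer where site approval lagged). Higher-arm cases are therefore probably few.
- If the Version 5.0 sentence in Protocol 5.1 refers only to subjects starting under that version, the conflict over changing strength disappears, though the 67 kg omission remains.

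A reader might infer that the error corrupts the safety comparison, with exposure acting as its denominator and tolerability credited to doses never taken. The documents do not support that. SAP 13.6.2.1 tabulates numbers and percentages of subjects by arm, with no rate per unit of exposure. The Appendix 6 columns (200/300 mg and 300/400 mg) place an affected subject in the correct arm at either strength.

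**Conclusion.** The rule in SAP 13.3.1 is wrong as written for one identifiable group: IMR-687 subjects of 60 to <67 kg who started under Version 4.0. For them it overstates daily dose by up to 50% in the lower arm and up to 33% in the higher arm. These are maxima. They assume the strengths inferred above and no change of strength during treatment. A switch at Version 5.0 would reduce them, and would also falsify the statement that one dose level holds throughout.

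How many subjects are affected, and so the shift in any arm mean, cannot be determined from the documents. The consequence is confined to the descriptive exposure summaries.

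A reader might also infer that apparent clearance and volume are biased, since the noncompartmental analysis uses only subjects sampled before Version 5.0 and divides by dose. The SAP does not state the source of that dose, so this can be raised as a question but not asserted.

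**What to change.** In SAP 13.3.1, define tablet dose level as the strength actually dispensed. Total exposure then becomes the sum over bottles of (tablets dispensed − tablets returned) × that bottle's strength, with average daily dose derived from it. This is right under either cut-off and under any change of strength during treatment.

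Reconcile SAP 13.3.1 with Protocol 5.1 on the weight cut-off in force by version, and on whether strength changed for subjects on treatment when Version 5.0 took effect.

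The cost is SAP wording and a merge on bottle identity once treatment codes are available. No new data should be needed. Protocol 10.2 says "Each bottle will contain a code that identifies the contents as either 100 mg IMR-687, 150 mg IMR-687, 200 mg IMR-687, or placebo", and SAP 13.1 shows that the accountability form records dosing dates by bottle. Adding mean mg/kg would be useful but is optional.
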